1.1 Background

Siddha system is one of the ancient systems of Indian medicine¹. This system focuses on leading a healthy life style based on physical, emotional, psychological and social wellbeing. In AYUSH systems the promotion of preventive approach to achieve the goal of being healthy is attained through holistic treatments. A pre-diabetic state (IFG, IGT, and both) of dysglycemia is defined as IGT which has a strong association with insulin resistance and increased risk of cardiovascular pathology. IGT may precede type 2 diabetes mellitus by many years. It is also a risk factor for mortality². Pre-diabetic stage is treated in contemporary western medicine with hypoglycemic drugs. But lifestyle modifications are treated separately and not approached holistically. Non-diabetic hyperglycemia that does not satisfy the diagnostic criteria for diabetes mellitus (DM) is generally known as prediabetes (preDM). It is generally agreed that all forms of diabetes pass through prediabetes state before escalating into full-blown diabetes⁷. Similar to DM, fasting plasma glucose (FPG) and oral glucose tolerance tests are both used independently as defining criteria for preDM^{7, 8}. Recently, hemoglobin A1c (HbA1c) has also been used in the diagnosis of preDM^{7, 9}. It is well-established that the risks of type 2 DM (T2DM) and cardiovascular disease are significantly increased in preDM subjects. The pooled relative risk for development of new diabetes is 6.02 in people with IGT, 4.70 in people with IFG, and 12.21 in people with both. Earlier evidences have proved that combined effect of diet, exercise and drugs (Metformin, Agarbose) are effective at preventive progression to DM from IGT subjects¹¹. According to DPP study intensive lifestyle intervention reduced the development of diabetes by 58%¹².

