The investigational drug is a polyherbal Siddha formulation. It is proven as an anti-diabetic^{3, 4, 6}. Some studies have investigated the possible anti-diabetic properties of combination drug in animal models, one in a high fructose diet induced and another in alloxan diabetic rats^{3, 5}. The results of these studies show that the administration of the extracts reduced the blood sugar level. Gallic acid is the component present in the composition of investigational drug having anti-diabetic activity⁷. More over the same studies highlighted the anti-oxidant and anti-obesity effects of this drug. These effects are assumed to play a major role to reduce the chances of transition of IGT patients to established diabetics. According to ICMR-INDIAB study conducted

in 2011, 3.9 million are estimated to be in the state of prediabetes in Tamil Nadu. Projections for the whole of India would be 77.2 million pre-diabetic patients¹⁰. So a poly-herbal formulation which is more effective, cost effective and safety among prediabetes patients.

According to the above references life style modification is done holistically in this study with the study drug.

2. Clinical Study Objectives:

2.1 Primary objective:

To assess the efficacy of Siddha formulation in the individuals having Impaired Glucose Tolerance (IGT) – (Munneerizhivu). If, during treatment or after treatment OGTT 2 hours remain between 126 mg/dl and 140 mg/dl, fasting blood sugar between 70 mg/dl and 100 mg/dl and HbA1c is $\leq 6.0\%$ it will be treated as successful outcome of the treatment.

2.2 Secondary objective:

To determine the Toxicological data of Siddha formulation

[figure not shown]
3 Study Design:

Open labelled Randomized Controlled Clinical Trial.

There will be two arms in this study. To one group is assigned life style modification and test drug and to the other group Life Style Modification (LSM). Randomization will be achieved through Random numbers.

3.1 Allocation to treatment:

The subjects will be allocated to the drug interventional group and LSM group based on the Random numbers generated by the computer.

Schematic representation of Study Design

5 Criteria for Inclusion:

Subjects in their 3rd to 6th decade only will be included in this study. Subjects falling in any one of the following criteria i.e. 2 hours OGTT should be between 140 mg and 199 mg. Glycated hemoglobin (HbA1C) > 6.0% and <6.5% and Blood sugar – Fasting > 100 and =< 125 mg/dl will be included.

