7.1 Screening procedures

The full details of history, physical examination, anthropometric measurements, 24-hours diet recall, physical activity of the patients will be recorded as per the proforma. OGTT is the critical investigation for this study and based on this the screening will be done. Investigations - HbA1c and Fasting blood sugar, Lipid profile, Liver function test, Renal function test, Electrolytes and Urine analysis will be taken before and after treatment and the reports will be recorded.

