10.1 Study endpoints

10.1.1 Primary endpoint

During treatment or after treatment OGTT 2 hours result is < 140 mg/dl, fasting blood sugar is < 100 mg/dl and HbA1c is < 6.0 % it will be treated as successful outcome of the treatment.

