8. The Diabetes prevention program (DPP) Research Group. *Diabetes care*, 2002, 25:2165-2171.

**OPEN LABELED RANDOMIZED CONTROLLED CLINICAL TRIAL ON
IMPAIRED GLUCOSE TOLERANCE –IGT (Munneerizhivu)**

FORM I - SCREENING PROFORMA

1. Code No (of clinical trial)
2. Centre: _____
3. Name of the Patient _____
4. S. No. of Patient _____
5. Gender Male (1) Female (2)
6. Date of Birth Age (Years)
7. Address _____

Mobile:

Phone no:

CRITERIA FOR INCLUSION

Yes (1)

No (0)

- | | | |
|---|----------------------|----------------------|
| 8. Age between 30 years and 60 years |  |  |
| 9. OGTT – After 2 hours < 140 mg and > 199 mg |  |  |
| 10. Glycated hemoglobin (HBA1C) >6.0% and <6.5% |  |  |

11. Blood sugar – Fasting > 100 and =< 125 mg/dl

CRITERIA FOR EXCLUSION

12. Age below 30 and above 60 years.

13. Malignant and accelerated hypertensive

14. CVS disorder (CAD)

15. Pregnant woman or the women planning to be pregnant in next six months

16. Lactating mothers

17. Secondary Diabetes mellitus

18. Patient undergoing regular treatment for Diabetes or for any other severe illness

19. CNS disorder e.g. encephalopathy

If yes to S.No.8-11 admit the patient into the study.

If admitted subject _____ No. _____

Date: _____

Signature of the Doctor _____

**OPEN LABELED RANDOMIZED CONTROLLED CLINICAL TRIAL ON
IMPAIRED GLUCOSE TOLERANCE –IGT (Munneerizhivu)**

FORM I A – SELECTION PROFORMA

1. Code No. (Clinical trial)
2. Centre :
3. Name of the Patient _____
4. S. No. of Patient _____
5. Gender Male (1) Female (2)
6. Date of Birth Age (Years)
7. Address _____

8. Educational status
Illiterate (1) Read & Write (2)
Educational qualifications _____ (3)
9. Occupation
Desk Work (1) Field Work (2) Others Specify _____
10. Income per capita per month in ₹ _____

Chief complaint with duration (if any) in days (mostly asymptomatic)

- | | Absent (0) | Present (1) |
|------------------------------------|----------------------|----------------------|
| 11. Polyuria (Excessive Urine) |  |  |
| If present, duration in days _____ | | |
| 12. Polyphagia (Excessive Hunger) |  |  |
| If present, duration in days _____ | | |
| 13. Polydipsia(Excessive Thirst) |  |  |
| If present, duration in days _____ | | |

Absent (0)

Present (1)

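### If participants may enter with one, two or three abnormal tests, the all-three-normal success comparison should be stratified by that number; neither Section 3.1 nor Section 10 uses it

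*Protocol*

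**What the plan says.** **Success.** Section 10.1.1 requires all three: "OGTT 2 hours result is < 140 mg/dl, fasting blood sugar is < 100 mg/dl and HbA1c is < 6.0" (per cent).

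**Entry.** Three descriptions differ.
- Section 5 opens with "Subjects falling in any one of the following criteria i.e. 2 hours OGTT should be between 140 mg and 199 mg", which reads as one abnormal test being enough. It then joins the other two tests with a conjunction: "Glycated hemoglobin (HbA1C) > 6.0% and <6.5% and Blood sugar – Fasting > 100 and =< 125 mg/dl will be included".
- Section 7.1 makes one test decisive: "OGTT is the critical investigation for this study and based on this the screening will be done".
- Form I lists age, OGTT, HbA1c and fasting sugar as items 8 to 11 and says "If yes to S.No.8-11 admit the patient into the study". Read literally, all three tests must be abnormal. Its OGTT item, as printed, asks for a value both below 140 and above 199 mg, which nobody can have.

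**Allocation.** Section 3.1: "The subjects will be allocated to the drug interventional group and LSM group based on the Random numbers generated by the computer". No stratum or block is named. Section 10.2 sets 30 per group.

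**Analysis.** Section 10 lists chi-square and an unspecified multivariate analysis for risk factors, ANOVA and the paired t test. It names no baseline factor for comparing success between the arms, and it leaves further analysis to depend on the results.

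**The concern.** Under the any-one rule, one participant succeeds by correcting a single marker and keeping two normal, while another must correct all three. Under the OGTT-based rule the same spread arises, because a person with an abnormal OGTT may have none, one or two further abnormal tests. The screening tests show the count for everyone before allocation.

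At 30 per arm, the group that happens to receive more one-abnormal participants can expect more successes with no drug effect. Ignoring the count also leaves a predictor in the error term. Section 10.2 gives no effect size or power for the 60 participants, so precision that costs nothing is worth taking.

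**Working it through.** The protocol gives no success rate, effect or power, so there is no figure of its own to reproduce.

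**Inputs from the protocol:** 30 per arm (10.2); success needs all three tests normal (10.1.1); unstratified allocation (3.1).

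**Assumptions:** 30 of the 60 enter on one abnormal test; success without drug effect is 50% for them and 12.5% or 15% for those with two or three; common drug odds ratio 4; two-sided 0.05.

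**1. Chance of imbalance.** Let X be the number of one-abnormal participants in the drug arm, hypergeometric (60 in total, 30 one-abnormal, 30 drawn). The arms differ by 2X − 30. P(|2X − 30| ≥ 6), that is 18 v 12 or worse, is 0.196. If the total is not fixed at 30 and each arm's count is binomial (30, 0.5), the probability is 0.155.

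**2. Size of the shift.** An excess of 6 changes the arm's one-abnormal share by 6/30 = 0.20 relative to the other arm.
- 0.20 × (0.50 − 0.125) = 0.075
- 0.20 × (0.50 − 0.15) = 0.070

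So the success difference moves by 7.0 to 7.5 points.

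**3. Against ordinary sampling error.** With equal strata, control success is (0.50 + 0.125)/2 = 0.3125. The standard error of the difference is √(2 × 0.3125 × 0.6875/30) = 0.120. The 7.5-point shift is 0.075/0.120 = about 0.6 of a standard error.

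**4. Power at odds ratio 4** (simulation, two strata, unstratified allocation):

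| Success, one v two or three abnormal | Unstratified | Mantel-Haenszel | Change, points |
|---|---|---|---|
| 50% v 12.5% | 56.5% | 64.0% | +7.5 |
| 50% v 15% | 61.0% | 66.7% | +5.7 |
| 60% v 10% | 44.8% | 56.8% | +12.0 |
| 40% v 15% | 65.1% | 68.4% | +3.3 |
| 40% v 30% (weak) | 74.2% | 73.7% | −0.5 |

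**5. Type I error.** About 5% for both tests under unstratified allocation: Mantel-Haenszel 4.9–5.2% here, and the unstratified test 4.6–5.3% in the three-strata runs of step 6.

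**6. Three strata instead of two.** Several entry mixes and log odds ratios of 1.0 to 2.0 were tried, with control success by one, two and three abnormal tests as shown.
- 40/30/20%: −1 to 0 points
- 50/25/10%: +2 to +5
- 60/30/10%: +3 to +8
- 70/30/5%: +7 to +14

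**7. Allocation or analysis?** With equal thirds, 60/30/10% and log odds ratio 1.5:
- unstratified allocation and test: 61.8%
- stratified allocation, unstratified test: 63.3%
- unstratified allocation, Mantel-Haenszel: 69.3%
- both stratified: 70.8%

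The analysis brings 7.5 points; stratified allocation adds 1.5.

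**8. All-three entry.** Every participant has three abnormal tests, so there is one stratum and nothing to gain.

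**The case against.** **The premise rests on one reading of an unresolved entry rule.** This stands as a condition. Form I read literally makes the count constant. However, its OGTT item cannot be satisfied as printed, and both Section 5 (any one) and Section 7.1 leave the count variable. The success limits are also worded differently in Sections 2.1 and 10.1.1, so both definitions need settling first.

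**Covariates belong in an SAP, which is not shown.** This stands in part. Section 10 does not expressly fix an unstratified test of success, and a later plan could name the factor. But the trial is open-label, the investigator analyses the data, and Section 10 leaves further analysis open to the results. If the factor is not named in advance, it can be chosen after outcomes are seen.

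**This is ordinary randomisation noise in an exploratory trial.** This is largely right. A reader might infer that imbalance biases the comparison or raises the false-positive rate. It does neither: type I error stays near 5%, and the illustrated shift is about 0.6 of a standard error. The harm is lost precision and a single result that may be harder to interpret.

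**The background figures do not show a gradient in success.** Correct. Section 1.1 gives relative risks of 6.02 for IGT, then "4.70 in people with IFG, and 12.21 in people with both". These concern progression to diabetes, not return to normal, and HbA1c is not part of that grouping. They support the gradient only indirectly.

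**Conclusion.** The point holds conditionally. If entry allows one, two or three abnormal tests, a known baseline factor that can strongly influence the primary endpoint goes unused. The cost is noise: about a 20% chance of a shift of 7 points or more (16% if the number entering on one abnormal test is itself random), and about 3 to 12 points of power at odds ratio 4 with a moderate to steep gradient. With a weak gradient there is nothing to gain and up to about 1 point to lose. The entry mix, the success rates and the odds ratio are all assumed.

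Two stronger readings are not supported. One is that the count largely decides success: the protocol gives no success rates by number of abnormal tests. The other is that stratified randomisation is essential: almost all the gain comes from the analysis. Under all-three entry there is no issue.

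**What to change.** 1. Reconcile the entry rule across Section 5, Section 7.1 and Form I, including the impossible OGTT item.
2. If the count can still vary, add one sentence to Section 10 and refer to it in 10.1.1: the proportions successful will be compared between arms with a Mantel-Haenszel test and a common risk difference, stratified by number of abnormal entry tests (one v two or three). Define abnormal as failing the final success limit at baseline. Otherwise a fasting value of exactly 100 mg/dl or an HbA1c of exactly 6.0%, which meets neither the Section 5 entry limit nor the 10.1.1 success limit, would be misclassified.
3. Optional: in 3.1, allocate in blocks within the two strata. Separate simple random lists would not secure balance. Do not do this without step 2: with stratified allocation and an unstratified test, simulated type I error fell to between 2.2% and 4.6%, and power sometimes fell too.

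**Cost.** One sentence, using tests already collected, with no extra patients or visits. Step 2 can still be adopted after enrolment has begun, provided it is fixed before outcomes are examined. The downside is a loss of up to about 1 point of power if the gradient is weak and, for step 3, incomplete blocks if a stratum is small.

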7.2 Follow-up Procedure

A prospective observation will be done for a period of one month after completion of the trial (6 months) by both groups. The drug intervention will be withdrawn in the drug group and LSM group will be on normal life style to measure the efficacy of the trial drug and LSM in both the groups. A comparison (physical assessment and blood sugar (OGTT) between the trial and non-trial period will be drawn in the outcome.

8. Safety and Efficacy Assessments

Liver function test and renal function test are recorded before and after trial drug administration to measure the safety of the drug. OGTT, HbA1c and blood glucose levels also measured for efficacy of the drug. Lipid profile is tested to measure the complementary benefit of the drug in microvascular end arterial diseases.

9. Adverse Event Reporting

If any adverse drug reaction or adverse event is reported, the study subject will be referred to the Pharmacovigilance cell of the study centre. According to the advice of the Pharmacovigilance cell withdrawal or continuation of the study will be determined.

10. Statistical Methods/Data Analysis

All the data will be entered in the Microsoft excel and the data will be analyzed using SPSS Version 16. Quantitative data shall be given in mean and standard deviation. Prevalence

shall be given in proportion with 95% confidence interval. Association with risk factors shall be analyzed using chi square test and multivariate analysis. Correlation shall be analyzed using Karl Pearson, with significant level ($P < 0.005$ or $P < 0.05$). Comparison between means with Annovatest, difference between means assessed by paired t test. Further analysis will be extended depending upon the results at the end of the study.

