10.2 Sample size determination

60 is the sample size as per the phase (Exploratory trial) of the clinical trial. 30 subjects will be enrolled in each group.

11. Criteria for Success of Treatment

Prevention or non-transformation of IGT to full blown diabetes which is measured by the primary end point will be considered as criteria stated above.

12. Trial Monitoring and Data Analyses

The progress of the trial will be monitored by the Guide. Data analysis will be done by the investigator.

13. Ethical Review

Institutional Ethical Committee (IEC) of participating centre is sought for clearance certificate before the project is initiated. Patient's information sheet and informed consent form will be submitted (Regional Language - Tamil) along with project proposal for approval by IEC. Both will be maintained in duplicate. Consent form will be given to the subject and will be enrolled with proper consent. One copy of Patient Information Sheet (PIS) will be given to the patient at the time of entry to the trial.

Reference:

1. Shukla s.s et al fundamental aspects and basic concepts of Siddha medicines. SYST-Re pharm 2011; 2:48-54.
3. American Diabetes Association. Diagnosis and classification of diabetes mellitus. *Diabetes Care*.2010; 33:S62–S69.
4. Unwin N et al, Impaired glucose tolerance and impaired fasting glycaemia: the current status on definition and intervention. *Diabet Med*. 2002; 19:708–723.
5. International Expert Committee. International Expert Committee report on the role of the A1C assay in the diagnosis of diabetes. *Diabetes Care*. 2009; 32:1327–1334.
6. Anjana RM et al, Prevalence of diabetes and prediabetes (impaired fasting glucose and/or impaired glucose tolerance) in urban and rural India: Phase I results of the Indian Council of medical research-India Diabetes (ICMR-INDIAB) study, 2011, *Diabetologia*, 54:3022-7.
7. Diagnosis, Prognosis, and Treatment of Impaired Glucose Tolerance and Impaired Fasting Glucose, McMaster University Evidence-based Practice Center, Hamilton, Ontario, Canada
<http://archive.ahrq.gov/downloads/pub/evidence/pdf/impglucose/impglucose.pdf>

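### Sections 2.1 and 10.1.1 define treatment success with different limits for all three measures, and the 126 mg/dl OGTT floor in 2.1 counts a larger glucose fall as failure

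*Protocol*

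**What the plan says.** Two sections of the Protocol say when a participant counts as a success.

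- Section 2.1 (Primary objective) requires "OGTT 2 hours remain between 126 mg/dl and 140 mg/dl, fasting blood sugar between 70 mg/dl and 100 mg/dl", and adds that if "HbA1c is $\leq 6.0\%$ it will be treated as successful outcome of the treatment".
- Section 10.1.1 (Primary endpoint) requires "OGTT 2 hours result is < 140 mg/dl, fasting blood sugar is < 100 mg/dl and HbA1c is < 6.0" per cent, and labels the result in the same words as 2.1.

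Section 11 (Criteria for Success of Treatment) describes success as not progressing to diabetes, "which is measured by the primary end point will be considered as criteria stated above". The OGTT entry criterion in section 5 is that "2 hours OGTT should be between 140 mg and 199 mg". The design (section 3) is "Open labelled Randomized Controlled Clinical Trial", with 30 participants per group (section 10.2). Section 12 states: "Data analysis will be done by the investigator".

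**The concern.** The primary objective and the primary endpoint should be the same rule. Here the two rules can give different success counts from the same data, and no sentence says which prevails.

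The OGTT limits matter most. Participants who qualify on OGTT start at 140 to 199 mg/dl. Under 2.1 someone who falls to 135 can succeed, while someone who falls to 110 cannot, although 110 is further from the entry range and fits the aim in section 11 better. The rule therefore works against whichever arm lowers glucose more.

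Treatment is known to participants and staff, the investigator analyses the data, and section 10 lets further analysis depend on the results. With two success rules in one protocol, the choice between them could be made after the counts are known.

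**Working it through.** **Step 1. Limits side by side.**

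| Measure | Section 2.1 | Section 10.1.1 |
|---|---|---|
| 2-hour OGTT (mg/dl) | 126 to 140 | < 140 |
| Fasting glucose (mg/dl) | 70 to 100 | < 100 |
| HbA1c (%) | ≤ 6.0 | < 6.0 |

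**Step 2. Both rules applied to example participants.** The 2.1 ranges are read as including their end points (an assumption). An exclusive reading would remove only the last two disagreements.

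| OGTT, fasting, HbA1c | 2.1 | 10.1.1 |
|---|---|---|
| 130, 90, 5.8 | success | success |
| 110, 90, 5.8 | failure | success |
| 130, 65, 5.8 | failure | success |
| 130, 90, 6.0 | success | failure |
| 140, 90, 5.8 | success | failure |
| 130, 100, 5.8 | success | failure |

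Each measure can change the classification by itself, and neither rule is simply a stricter form of the other.

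**Step 3. How often the OGTT floor bites.** The Protocol gives no on-treatment mean or SD, so these are assumed: normal values with mean m of 120 to 140 and SD s of 15 to 25 mg/dl. Among participants below 140, the share also below 126 is Φ((126 − m)/s) / Φ((140 − m)/s).

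- Lowest, m = 140 and s = 15: Φ(−0.933)/Φ(0) = 0.175/0.500 = 0.351.
- Middle, m = 130 and s = 20: Φ(−0.20)/Φ(0.50) = 0.421/0.691 = 0.61.
- Highest, m = 120 and s = 25: Φ(0.24)/Φ(0.80) = 0.595/0.788 = 0.755.

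The range is 35% to 76%.

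**Step 4. Effect on the comparison, OGTT component alone.** For each arm, the 10.1.1 proportion is Φ((140 − m)/s), and the 2.1 proportion is Φ((140 − m)/s) − Φ((126 − m)/s). With test mean 120, control mean 135 and SD 20, 10.1.1 gives 84.1% v 59.9% and 2.1 gives 22.3% v 27.2%. Differences, test minus control, in percentage points (taken before rounding):

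| Test v control mean | 10.1.1, SD 15 / 20 / 25 | 2.1, SD 15 / 20 / 25 |
|---|---|---|
| 120 v 135 | +27.8 / +24.3 / +20.9 | −10.3 / −4.9 / −2.7 |
| 125 v 140 | +34.1 / +27.3 / +22.6 | −1.0 / −0.5 / −0.2 |
| 130 v 145 | +37.8 / +29.0 / +23.5 | +8.6 / +4.0 / +2.2 |
| 135 v 150 | +37.8 / +29.0 / +23.5 | +15.9 / +7.9 / +4.4 |
| 120 v 150 | +65.6 / +53.3 / +44.4 | +5.6 / +3.0 / +1.7 |

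The difference is smaller under 2.1 in every row. It reverses at 120 v 135, is close to zero at 125 v 140, and keeps its sign in the other three rows.

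**Step 5. HbA1c at the limit.** With one-decimal reporting, assumed mean 5.8 to 6.2 and SD 0.2 to 0.3, the chance of a reading of exactly 6.0 is P(5.95 to 6.05). It runs from 0.106 (mean 5.8 or 6.2, SD 0.3) to 0.197 (mean 6.0, SD 0.2). Out of 30 that is 3.2 to 5.9 participants, who meet this component under 2.1 only.

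**The case against.** The strongest reply is that section 11 already settles the matter: it measures success by the primary endpoint, and only 10.1.1 carries that heading. On this view 2.1 is a badly worded sentence in a 60-person exploratory trial. This stands in part. 10.1.1 is the more natural rule, but 2.1 attaches the same success label to other limits in the primary objective, and nothing withdraws it.

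A second reply is that the harm to the comparison depends on assumed means. This stands. A reader might infer from the 120 v 135 case that the floor would reverse the trial's result. The Protocol gives no expected means, the other rows in the table show no reversal or almost none, and success needs all three measures, not OGTT alone.

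A third reply is that the 2.1 limit for HbA1c is the better one: section 5 asks for HbA1c above 6.0% at entry, so ≤ 6.0% is its exact complement. That is a fair argument about which limit to choose. It is no reason to keep two.

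A reader might also infer a safety gap, because under 10.1.1 a fasting value below 70 mg/dl meets the fasting component while section 8 says "Liver function test and renal function test are recorded before and after trial drug administration to measure the safety of the drug" and places glucose under efficacy. The document does not support this as an error. It nowhere calls 70 mg/dl a harm limit, Form III records fasting glucose at the visits from day 0 to day 180, section 9 refers reported adverse events to the Pharmacovigilance cell, and a count of low values is a reporting detail that a SAP may cover.

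**Conclusion.** The point holds as a contradiction within the Protocol. All three limits differ, the rules disagree in both directions, and the 126 mg/dl floor in 2.1 is wrong as written. These conclusions need no assumption.

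The size does rest on assumptions. For normal OGTT values with mean 120 to 140 and SD 15 to 25, 35% to 76% of those below 140 would fail the 2.1 floor. On the OGTT component, differences of +20.9 to +65.6 points under 10.1.1 become −10.3 to +15.9 points under 2.1. Reversal is possible but is not a forecast.

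A reader might also turn the 35% to 76% into an equal loss of overall successes under 2.1. That does not follow. 2.1 also gains participants whose HbA1c is exactly 6.0%, and the net change needs the joint distribution of the three measures, which the Protocol does not give. Nor does the document show any intention to choose between the rules after the fact; it only leaves that open.

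**What to change.** Replace the success sentence in section 2.1 with the definition in 10.1.1: 2-hour OGTT < 140 mg/dl with no lower limit, fasting glucose < 100 mg/dl and HbA1c < 6.0%. One rule then applies in 2.1, 10.1.1 and 11.

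The cost is one sentence, with no new test, visit or analysis. The downside is that a participant with HbA1c of exactly 6.0% counts as a failure, although that value lies outside the entry range. The change does not settle at which visit success is judged, which both sections leave open as during or after treatment.

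### HbA1c of exactly 6.0% and fasting glucose of exactly 100 mg/dl fail the primary endpoint in Section 10.1.1, although Section 5 does not count them as raised and Section 2.1 accepts HbA1c of 6.0% as success

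*Protocol*

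**What the plan says.** Four places in the Protocol bear on the boundary.

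- **Section 10.1.1 (primary endpoint).** Success needs three results together. The first is "During treatment or after treatment OGTT 2 hours result is < 140 mg/dl"; the other two are that "fasting blood sugar is < 100 mg/dl and HbA1c is < 6.0"%. All three limits are strict.
- **Section 5 (inclusion).** The entry ranges are "Glycated hemoglobin (HbA1C) > 6.0% and <6.5"% for HbA1c and "Fasting > 100 and =< 125 mg/dl will be included" for fasting glucose. Exactly 6.0% and exactly 100 mg/dl lie outside them. The sentence opens with "Subjects falling in any one of the following criteria", which lets a person enter on one raised test.
- **Section 2.1 (primary objective).** The same successful outcome is defined with a different HbA1c limit: "HbA1c is $\leq 6.0\%$ it will be treated as successful outcome of the treatment". Fasting glucose is to lie between 70 and 100 mg/dl, without saying whether 100 itself counts, and the 2-hour OGTT between 126 and 140 mg/dl.
- **Form I (screening).** Items 8 to 11 cover age, OGTT, HbA1c and fasting glucose, followed by "If yes to S.No.8-11 admit the patient into the study". This asks for all of them, so every entrant would have both HbA1c and fasting glucose raised.

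Section 10.2 sets 60 participants, 30 per group. It gives no expected success rate, standard deviation or effect size.

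**The concern.** The three success conditions are joined by 'and', so one reading on the boundary decides a participant's primary outcome. Someone who ends with no test in its Section 5 raised range can still be a failure. At HbA1c 6.0% the Protocol also gives two opposite answers to whether the HbA1c condition is met.

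The limits are round numbers close to where this population lies by design. If HbA1c is reported to one decimal, 6.0% would be a common reading. With 30 per arm, one or two reclassified participants are a visible share of the successes. The trial is open label and Section 12 has the investigator analyse the data. If the two definitions remain, the choice between them could be made after the results are known.

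**Working it through.** **1. The limits side by side**

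| Test | Raised at entry (Section 5) | Success (10.1.1) | Success (2.1) | Boundary value |
|---|---|---|---|---|
| HbA1c | > 6.0% and < 6.5% | < 6.0% | <= 6.0% | 6.0%: not raised; fails 10.1.1; meets 2.1 |
| Fasting | > 100 and <= 125 mg/dl | < 100 mg/dl | 70 to 100 mg/dl, end point not settled | 100: not raised; fails 10.1.1; unclear in 2.1 |
| 2-hour OGTT | between 140 and 199 mg/dl | < 140 mg/dl | 126 to 140 mg/dl | no gap if 140 counts as within the entry range |

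**2. A single case.** A participant ends with OGTT 130 mg/dl, fasting 95 mg/dl and HbA1c 6.0%. Section 5: no test is raised. Section 2.1: success. Section 10.1.1: failure. This needs no assumption.

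**3. Who can be affected.** Under Section 5's one-criterion wording, a person may enter on OGTT with HbA1c already at 6.0%, and later fail on a test that was not raised at entry. Under Form I that person is not admitted. The gap then affects only people whose raised value fell to the boundary, for example from 6.2% to 6.0%.

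**4. Size.** The plan has no figure to reproduce: 30 + 30 = 60 is all that can be checked. The size needs inputs that the documents do not give.

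Assumed outcome values: HbA1c mean 5.8, 6.0 or 6.2% with SD 0.25-0.35; fasting mean 95, 100 or 105 mg/dl with SD 9; OGTT mean 145 mg/dl with SD 28; pairwise correlation 0.4; one assessment; fasting and OGTT rounded to 1 mg/dl. The method is a trivariate normal simulation with 400,000 draws, rounded to reporting precision.

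- P_strict = P(OGTT < 140, fasting < 100, HbA1c < 6.0)
- P_incl = P(OGTT < 140, fasting <= 100, HbA1c <= 6.0)
- Relative loss = 1 - P_strict / P_incl
- People lost per arm = 30 x (P_incl - P_strict)

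With HbA1c reported to 0.1%, about 10-16% of HbA1c readings are exactly 6.0% and about 4% of fasting readings are exactly 100. The relative loss by mean HbA1c is:

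| Mean HbA1c | Relative loss |
|---|---|
| 5.8% | 10-15% |
| 6.0% | 17-24% |
| 6.2% | 25-38% |

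- Mid-grid example (mean 6.0, SD 0.25, fasting mean 100): P_strict 17.2%, P_incl 22.3%. Loss 1 - 0.172/0.223 = 0.23; 30 x 0.051 = 1.5 people per arm.
- Top of the range (mean 6.2, SD 0.25, fasting mean 105): 6.0% against 9.7%. Loss 1 - 0.060/0.097 = 0.38, but only 30 x 0.037 = 1.1 people per arm.
- Over the whole grid: about 0.8-1.8 people per arm.

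With HbA1c reported to 0.01%, the relative loss is about 4-12%, or 0.2-0.6 people per arm.

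**5. Sensitivity.** A wider grid treats HbA1c and fasting glucose as independent and leaves out the OGTT condition (HbA1c mean 5.6-6.2, SD 0.2-0.4; fasting mean 92-107, SD 7-13). It gives 6-63% at 0.1% precision (median about 24%) and 4-25% at 0.01% (median about 9%). The 63% is 1.5% against 4.0%, a difference of 2.5 percentage points.

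**The case against.** The strongest reply is that Section 5 decides who may enter. It does not declare 6.0% or 100 mg/dl normal, and a response limit stricter than the entry limit is an ordinary design choice. That stands as far as Section 5 alone goes: exact complements are not obligatory. It does not answer Section 2.1, which defines the same success with the inclusive HbA1c limit. The Protocol cannot mean both.

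A reader might infer four stronger things, none of which the documents support.

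- *That people are failed on tests that were never raised.* This follows only from Section 5's one-criterion wording. Form I requires all items. Form I is not decisive either, since its OGTT item as printed (below 140 and above 199) cannot be met by any value; the entry rule is simply unsettled. The simulation above draws outcome values only and does not isolate this mechanism. An illustration that adds a baseline draw takes entry on OGTT 140-199 with the other tests below their upper entry limits, baseline means 150/102/6.05 (OGTT/fasting/HbA1c), SDs 28/9/0.3, baseline-outcome correlation 0.5-0.8, and no to moderate improvement. It attributes about 12-39% of the lost successes to a boundary test not raised at entry, a relative loss of about 2-9%.
- *That the success rate is understated by 10-38%.* The Protocol defines no true success rate to fall short of, and every input to that range is assumed. The limits are written to one decimal, but Form III leaves the HbA1c entry blank with no stated precision. Section 10.1.1 also allows success during or after treatment, and Form III's visit note places HbA1c at days 90 and 180. The calculation uses one assessment.
- *That 10.1.1 is stricter than 2.1 overall.* It is not. Section 2.1 also requires OGTT of at least 126 mg/dl. For assumed OGTT means of 120-150 and SDs of 20-30, the 10.1.1 OGTT limit alone passes about 1.5 to 4.1 times as many people as the 2.1 window.
- *That the comparison is biased.* The same rule applies to both arms. It lowers the success proportion in each against an inclusive rule and shows no bias between them.

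**Conclusion.** The boundary defect holds on the text alone. Sections 2.1 and 10.1.1 contradict each other at HbA1c 6.0%, and 10.1.1 fails two values that Section 5 does not count as raised. Against an inclusive rule, the strict rule can only lower the number of successes.

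The size is conditional: about 10-38% fewer successes at 0.1% HbA1c precision and 4-12% fewer at 0.01%, under the assumed distributions. In people, that is roughly 0.2 to 1.8 per arm of 30. The figure shows that the choice of symbol can matter in a trial this small; it does not estimate what this trial would lose.

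**What to change.** Before any outcome data are seen, reconcile Sections 2.1, 5, 10.1.1 and Form I, and state one success definition in one place, with the other passages referring to it. For the endpoint, HbA1c <= 6.0%, as 2.1 already has it, and fasting <= 100 mg/dl would make the outcome limits the complement of the Section 5 limits. The OGTT limit of < 140 mg/dl can stay once Section 5 says whether 140 is included. State the reporting precision for HbA1c (for example 0.1%) and for fasting glucose, so that the same rounding applies at entry and outcome.

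If the sponsor wants the strict limits, keep them, give the reason, and correct 2.1 to match. The contradiction then goes, and the gap to Section 5 becomes a stated choice. Whether entry needs one raised test or all of them must also be settled between Section 5 and Form I; this point does not depend on which.

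The cost is two symbols in 10.1.1, a sentence on precision and matching wording elsewhere. No new data are needed. The downside is that boundary values would count as success in both arms.
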